- 16. All safety assessments performed at screening must be normal and checked against the inclusion/exclusion criteria prior to study drug administration at visit 4. Similarly, it is recommended to review relevant safety assessments prior to dosing at visit 11. Participants will be observed for 2 hours after receiving the SC dose of study drug. Safety labs may be repeated if any concerns, per PI discretion.
- 17. A full physical exam must be done at screening, visits 4, 11, and 15. A limited relevant physical exam will be done at the remaining visits, per PI judgement, depending on presentation of the participant. Additional relevant physical exams may be conducted during and after completion of the EEU challenges, per PI discretion.
- 18. Vital signs include systolic and diastolic blood pressure, respiratory rate, heart rate, and temperature. Vital signs will be collected in a seated position.
 - *On visit 4 (day 1) and visit 11, vital signs are taken prior to study drug administration and at 2 hours (approximately ± 15 min) after completion of study drug administration.
 - Additional vital signs may be recorded during and after completion of the EEU challenges, per PI discretion.
- 19. Inclusion/ exclusion criteria will be verified only to document any changes, not to determine study eligibility.
- 20. Testing for COVID-19 or other respiratory infections may be performed at visits, per site local protocols.
- 21. If the urine pregnancy test is positive, the site must perform a serum pregnancy test for confirmation. For visit 4 (randomization) if a serum pregnancy test must be performed, study drug cannot be administered unless the serum pregnancy test is negative. For all EEU visits (visits 2, 3, 6, 7, 8, 9, 13, and 14) and early termination, if a pregnancy test must be performed, EEU and associated procedures cannot be performed unless the pregnancy test

- is negative. Urine pregnancy test can be performed on day -1 of EEU visits and early termination, at the investigator's discretion.
- 22. Electrocardiogram will be performed locally by the site.
- 23. Spirometry will be performed locally by the site. *Spirometry at screening and randomization is required for all participants for eligibility. At other visits, spirometry and/or peak expiratory flow (PEF) may be performed for participants, per PI judgement.

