10.3. Vital Signs

The following vital signs parameters will be recorded pre-dose and 2 hours post dose, and summarized according to the Schedule Events in Section Section 14.2:

- Temperature
- Systolic/diastolic blood pressure
- Heart rate
- Respiration rate

Summaries of vital sign variables will include:

- Descriptive statistics of vital sign variable and change from baseline by visit by treatment group
- The number (n) and percentage (%) of subjects with treatment-emergent PCSV

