10.7. Biomarker Data

Exploratory biomarker data may be described in a separate exploratory analysis plan. Analyses may include (but are not limited to) evaluating relationships between biomarkers and clinical responses. Exploratory biomarker variables may include (but are not limited to) serum allergenspecific IgE levels (birch, Bet v 1, Bet v 2, and other common allergens) and basophil activation. Relevant biomarker data analyses may be included in the CSR and/or a separate biomarker report.

11. **DATA CONVENTIONS**

11.1. **Definition of Baseline for Efficacy/Safety Variables**

Unless otherwise specified, the Baseline assessment for all measurements will be the latest available valid measurement taken prior to the administration of investigational product. The following rules specify the determination of baseline by both date/time information:

• The date and time of first injection will be used to determine the baseline for the AE, lab, PK and ADA data.

Date: May 31, 2023

• Only the date of first injection will be used to determine the baseline for other data except the AE, lab, PK and ADA data.

For the efficacy endpoints, the baseline is defined as following:

- For all symptom scores (TNSS or TOSS) collected in EEU chambers, the baseline is defined as the mean of the corresponding measurements (2 to 6 hours) during the allergen EEU challenge in screening period. The baseline visit for Birch is Visit 2, and the baseline visit for Oak is Visit 3.
- For daily e-diary scores (daily TNSS, daily TOSS, DMS, daily TSS, daily CSMS, RQLQ(S), PFASQ, and outdoor questionnaire), there are two baselines defined, pretreatment baseline and pre-season baseline.
 - The pre-treatment baseline is defined as the average of the daily score during the screening period before the first dose. All days with scores during the screening period will be used to calculate the average, except for the day of and one day following EEU challenge.
 - The pre-season baseline is defined as the average of the daily score start from the Visit 10 to the day before the local BPS, except for the day of and one day following EEU challenge.

The number of non-missing daily records must be at least 3 after excluding the records happening on the same day and the next day of the EEU visit for pre-treatment and preseason baseline (both pre-treatment baseline) calculation. If the baseline value is smaller than 1, the baseline will be set to 1.

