- 13. Visit timeframes in Part B (visits 10 to 15) may vary based on the timing and duration of the anticipated BPS. End-of-season EEU challenge (visit 14) should occur after the end of the protocol-defined end of the BPS.
- 14. Dose #2 should be administered at minimum 12 weeks after dose #1.
- 15. Participants will be contacted within 1 day (visit 12) after dose 2 (visit 11) via telephone to monitor safety trends.
- 16. All safety assessments performed at screening must be normal and checked against the inclusion/exclusion criteria prior to study drug administration at visit 4. Similarly, it is recommended to review relevant safety assessments prior to dosing at visit 11. Participants will be observed for 2 hours after receiving the SC dose of study drug. Safety labs may be repeated if any concerns, per PI discretion.
- 17. A full physical exam must be done at screening, visits 4, 11, and 15. A limited relevant physical exam will be done at the remaining visits, per PI judgement, depending on presentation of the participant. Additional relevant physical exams may be conducted during and after completion of the EEU challenges, per PI discretion.
- 18. Vital signs include systolic and diastolic blood pressure, respiratory rate, heart rate, and temperature. Vital signs will be collected in a seated position.
 - *On visit 4 (day 1) and visit 11, vital signs are taken prior to study drug administration and at 2 hours (approximately ±15 min) after completion of study drug administration.
 - Additional vital signs may be recorded during and after completion of the EEU challenges, per PI discretion.
- 19. Inclusion/ exclusion criteria will be verified only to document any changes, not to determine study eligibility.
- 20. Testing for COVID-19 or other respiratory infections may be performed at visits, per site local protocols.

21. If the urine pregnancy test is positive, the site must perform a serum pregnancy test for confirmation. For visit 4 (randomization) if a serum pregnancy test must be performed, study drug cannot be administered unless the serum pregnancy test is negative. For all EEU visits (visits 2, 3, 6, 7, 8, 9, 13, and 14) and early termination, if a pregnancy test must be performed, EEU and associated procedures cannot be performed unless the pregnancy test is negative. Urine pregnancy test can be performed on day -1 of EEU visits and early termination, at the investigator's discretion.

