generon Pharmaceuticais, inc	c. Protocol	: K3/13-3/14-3/13	O-ALG-	ZIIII Amenan	nent I

Parameter	PCSV	Comments
RBC	<4 Tera/L and ≥ 4 Tera/L at baseline for Male; <3 Tera/L and ≥ 3 Tera/L at baseline for Female ≥7 Tera/L and <7 Tera/L at baseline for Male; ≥6 Tera/L and <6 Tera/L at baseline for Female	Unless specifically required for particular drug development, the analysis is redundant with that of Hb.
Platelets	<100 Giga/L and ≥100 Giga/L at baseline ≥700 Giga/L and < 700 Giga/L at baseline	International Consensus meeting on drug-induced blood cytopenias, 1991. Two independent criteria
Vital signs		
HR	≤50 bpm and decrease from baseline ≥20 bpm ≥120 bpm and increase from baseline≥20 bpm	
SBP	≤95 mmHg and decrease from baseline ≥20mmHg ≥160 mmHg and increase from baseline ≥20 mmHg	
DBP	≤45 mmHg and decrease from baseline ≥10 mmHg ≥110 mmHg and increase from baseline ≥10 mmHg	
Respiratory rate	< 12 per minutes and ≥12 per minute at baseline >20 per minute and ≤20 per minute at baseline	
Temperature	>= 100.4 °F/38.0 °C	

14.4. **Search Criteria for TEAE of Special Interest**

AESI	Search Criteria
Systemic or severe hypersensitivity reactions	Narrow SMQ for hypersensitivity Note: Anaphylaxis will be prospectively analyzed using the criteria discussed in the statement paper from the Second Symposium on the definition and Management of Anaphylaxis (Sampson, 2006). This would include manual adjudication of relevant PTs performed by the study medical monitor, before database lock

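### SAP 11.1 sets the vital-sign baseline by date alone, so it cannot separate the pre-dose from the 2-hour post-dose reading on day 1 and can yield a post-dose or a screening baseline

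*SAP*

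**What the plan says.** SAP 11.1 first gives a general definition: "the Baseline assessment for all measurements will be the latest available valid measurement taken prior to the administration of investigational product". It then gives two operating rules. One is "The date and time of first injection will be used to determine the baseline for the AE, lab, PK and ADA data". The other is "Only the date of first injection will be used to determine the baseline for other data except the AE, lab, PK and ADA data". Vital signs are not in the list that uses time. Efficacy scores have their own baseline definitions further down the section; vital signs do not.

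SAP 10.3 says of vital signs: "The following vital signs parameters will be recorded pre-dose and 2 hours post dose". Footnote 18 to the protocol's schedule of events covers both dosing visits, 4 and 11, of which the former is day 1: "vital signs are taken prior to study drug administration and at 2 hours (approximately ± 15 min) after completion of study drug administration". Footnote 18 in SAP 14.2 repeats this. Protocol 8.2.3.1 mentions only pre-dose collection, but it defers to the schedule of events, where footnote 18 adds the 2-hour reading.

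Two outputs use this baseline. SAP 10.3 plans "Descriptive statistics of vital sign variable and change from baseline by visit by treatment group", and it plans counts of participants with treatment-emergent PCSVs. SAP 14.3 sets the thresholds; the low systolic criterion is "≤95 mmHg and decrease from baseline ≥20mmHg". SAP 10 ties treatment-emergent PCSVs to a single study baseline.

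**The concern.** The general definition needs to know which reading came before the injection. For vital signs, the operating rule discards the information that would show it. Two programmers could follow SAP 11.1 in good faith and derive different baselines for the same participant.

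If the 2-hour reading is taken as baseline, an acute change after dose #1 vanishes from the tables meant to show it, and every later change is measured from a post-dose value. The 2-hour reading is the only vital-sign check scheduled after the injection on day 1; the next is at visit 6. Protocol 3.3 names systemic hypersensitivity as an important potential risk, so these tables should be unambiguous.

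**Working it through.** The plan states no figure on this point, so there is nothing to reproduce. The check applies the rule as written to the scheduled records.

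**Step 1: which rule applies.** Time is used for AE, laboratory, PK and ADA data. Everything else, hence vital signs, uses the date of first injection only.

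**Step 2: what carries that date.** A participant assessed as scheduled has two vital-sign sets dated day 1, one pre-dose and one about 2 hours post-dose. A date cannot order them.

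**Step 3: the possible readings.** The systolic pressures below are assumptions for illustration, not values from the documents: screening 122, Visit 4 pre-dose 120, Visit 4 at 2 hours 92, Visit 6 118, Visit 11 at 2 hours 94 mmHg. Change = value − baseline. The low systolic PCSV needs a value of 95 or less and a fall of at least 20.

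| Reading of SAP 11.1 | Baseline | Visit 4, 2 h | Visit 6 | Visit 11, 2 h |
|---|---|---|---|---|
| A. Latest record dated on or before the injection date | 92 (2 h post-dose) | 92 − 92 = 0, not flagged | 118 − 92 = +26, not flagged | 94 − 92 = +2, not flagged |
| B. Latest record dated strictly before the injection date | 122 (screening) | 92 − 122 = −30, flagged | 118 − 122 = −4, not flagged | 94 − 122 = −28, flagged |
| C. Opening sentence governs | 120 (pre-dose) | 92 − 120 = −28, flagged | 118 − 120 = −2, not flagged | 94 − 120 = −26, flagged |

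C is the stated intent, but it needs a clock time or a nominal time-point label, and the date-only rule uses neither.

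**Step 4: the general result under A.** The 2-hour change is a value minus itself, so it is always 0. The SAP 14.3 criteria require a change of at least 20 bpm for heart rate, 20 mmHg for systolic and 10 mmHg for diastolic pressure, so none can be met at that time point. The respiratory-rate criteria need a value below 12 with a baseline of at least 12, or above 20 with a baseline of at most 20. Neither can hold when value and baseline are the same reading. Because there is one study baseline, the shifted reference carries through dose #2, as the Visit 11 column shows.

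**Step 5: what is not touched.** The temperature criterion in SAP 14.3 has no baseline condition. AE and AESI capture does not use the vital-sign baseline.

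**The case against.** The strongest reply is that the opening sentence of SAP 11.1 already forbids a post-dose baseline and the rules beneath it do not repeal it. That stands against one tempting inference, that the SAP prescribes a post-injection baseline. It does not; it contradicts itself and permits one. The reply does not remove the defect, because the operating rule for vital signs cannot carry out the opening sentence.

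A reader might also infer that SAP Table 4 settles the matter, since it gives baseline as study day 1 or earlier and starts the next window on day 2. It does not. SAP 11.4 applies those windows only when scheduled-visit data are unavailable, and the same baseline entry appears for laboratory and ADA data, which do use clock time.

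The two readings are distinguishable by label: SAP 10.3 names both, and Protocol 10.4.5.2 calls for change from baseline to each scheduled time point. This supports reading C as the intent, but SAP 11.1 never says that the label is to be used.

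Finally, a reader might infer that acute hypersensitivity could go unseen. The documents do not support that. Participants are observed for 2 hours after dosing, and systemic or severe hypersensitivity is an AESI with 24-hour reporting (Protocol 9.1.3). AESIs are found by CRF flag and SMQ search with clinical adjudication (SAP 10.1.1), and Protocol 9.1.1 sends vital-sign findings that are symptomatic, need corrective treatment or are judged to be AEs into AE reporting. Absolute vital-sign values are also summarized.

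**Conclusion.** The point holds as an internal inconsistency in SAP 11.1 that should be corrected. For vital signs, the stated rule cannot identify the pre-dose reading; taken literally, it gives either the 2-hour post-dose value or a screening value. Acute changes are hidden under only one of the three readings (A). Under B the fall stays visible, but the pre-dose reading is lost.

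The impact is confined to descriptive change-from-baseline tables and to the heart-rate, blood-pressure and respiratory-rate PCSVs. No efficacy result or hypothesis test is involved.

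The baseline is undetermined for each participant with both day 1 readings, and the design target is about 300 participants. It would be wrong to infer that about 300 results would change. A flag is lost or shifted only where vital signs move enough by 2 hours or sit near a threshold, and the documents give no data to count such participants. Protocol 3.3 reports no systemic hypersensitivity or anaphylaxis among 229 people given a single dose of the 3-mAb cocktail. The example rests on assumed pressures and shows the mechanism, not a frequency.

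**What to change.** In SAP 11.1, add vital signs to the data types whose baseline uses the date and time of first injection. Alternatively, define their baseline as the last pre-dose record, which is the scheduled Visit 4 pre-dose reading. In SAP 10.3, state that the 2-hour readings at Visits 4 and 11 are summarized and screened for PCSVs as post-baseline time points. The fallback windows in Table 4 need no change.

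The cost is a line of SAP wording in each of two sections and one derivation rule in the programming. Both readings are already scheduled, so no new data are needed.

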- 24. Daily TNSS, TOSS, and DMS assessments will being collected by e-diary during screening and in Part B from visit 10 to visit 15. The e-diary is returned at visit 15.
- 25. Screening baseline assessment: e-diary assessments for symptoms and allergy rescue medication use should be obtained for an approximate 2-week period or longer (at minimum 1 week) starting after the screening birch EEU challenge until randomization (visit 4) in eligible subjects. It is recommended that it is performed outside of relevant pollen seasons when pollen-allergic subjects are not significantly symptomatic due to other pollens.
- 26. Pre-season baseline assessment: e-diary assessments for symptoms and allergy rescue medication use should be obtained approximately 2 weeks or longer up (at minimum 1 week) to receipt of dose 2 given ahead of the anticipated BPS (starting at visit 10 [Part B]) and prior to receiving dose 2 at visit 11 ahead of the BPS).
- 27. Allergy relieving rescue medications, as needed, should be dispensed at the end of symptom score collection on visits 2, 3, 6, 7, 8, and 9. Rescue medications are dispensed starting at visit 10 for management of symptoms during the pollen season up to visit 15.
- 28. RQLQ(S) is administered weekly starting at visit 2 (during screening baseline assessment period) and then weekly using an e-diary in Part B starting at visit 10 until visit 15.
- 29. Pollen food allergy questionnaire (PFASQ) is administered every 2 weeks at baseline starting at visit 2 (during screening baseline assessment period) and then every 2 weeks in Part B starting at visit 10 until visit 15.
- 30. Outdoor time questionnaire is administered daily at baseline starting at visit 2 (during screening baseline assessment period) and then daily using an e-diary in Part B starting at visit 10 until visit 15.
- 31. Basophil activation test (BAT) samples may be collected from approximately 100 randomized participants (subset of the total enrolled population at one or both EEU sites; additional samples may be collected at the screening EEU visit to account for potential screen failures). The initial samples for a BAT assay are to be collected prior to the administration of study drug and subsequent BAT assay samples are to be collected prior to the respective EEU challenges.
- 32. Samples are to be collected prior to the administration of study drug and prior to EEU challenges, when applicable.

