8.2.2.8. Standardized Rhinoconjunctivitis Quality of Life Questionnaire for Ages 12+

RQLQ(S) will be recorded at the time points according to Table 1. The RQLQ(S) is a self-administered questionnaire to measure health-related quality of life in those 12 years of age and above, as a result of perennial or seasonal allergic rhinitis. There are 28 items with 1-week recall on the RQLQ(S) in 7 domains: activity limitation, sleep problems, nasal symptoms, eye symptoms, non-nasal/eye symptoms, practical problems, and emotional function. The RQLQ(S) responses are based on a 7-point Likert scale with responses ranging from 0 (not troubled) to 6 (extremely troubled). The overall RQLQ(S) score is the mean of all 28 responses and the individual domain scores are the means of the items in those domains. Higher scores indicated more health-related quality of life impairment (lower scores were better).

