- 22. Electrocardiogram will be performed locally by the site.
- 23. Spirometry will be performed locally by the site. *Spirometry at screening and randomization is required for all participants for eligibility. At other visits, spirometry and/or peak expiratory flow (PEF) may be performed for participants, per PI judgement.
- 24. Daily TNSS, TOSS, and DMS assessments will being collected by e-diary during screening and in Part B from visit 10 to visit 15. The e-diary is returned at visit 15.
- 25. Screening baseline assessment: e-diary assessments for symptoms and allergy rescue medication use should be obtained for an approximate 2-week period or longer (at minimum 1 week) starting after the screening birch EEU challenge until randomization (visit 4) in eligible subjects. It is recommended that it is performed outside of relevant pollen seasons when pollen-allergic subjects are not significantly symptomatic due to other pollens.
- 26. Pre-season baseline assessment: e-diary assessments for symptoms and allergy rescue medication use should be obtained approximately 2 weeks or longer up (at minimum 1 week) to receipt of dose 2 given ahead of the anticipated BPS (starting at visit 10 [Part B]) and prior to receiving dose 2 at visit 11 ahead of the BPS).
- 27. Allergy relieving rescue medications, as needed, should be dispensed at the end of symptom score collection on visits 2, 3, 6, 7, 8, and 9. Rescue medications are dispensed starting at visit 10 for management of symptoms during the pollen season up to visit 15.
- 28. RQLQ(S) is administered weekly starting at visit 2 (during screening baseline assessment period) and then weekly using an e-diary in Part B starting at visit 10 until visit 15.
- 29. Pollen food allergy questionnaire (PFASQ) is administered every 2 weeks at baseline starting at visit 2 (during screening baseline assessment period) and then every 2 weeks in Part B starting at visit 10 until visit 15.
- 30. Outdoor time questionnaire is administered daily at baseline starting at visit 2 (during screening baseline assessment period) and then daily using an e-diary in Part B starting at visit 10 until visit 15.

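### SAP 11.1 applies a three-record baseline minimum to the weekly RQLQ(S) and two-weekly PFASQ, which the nominal two-week screening run-in cannot supply

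*SAP*

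**What the plan says.** SAP Section 11.1 groups the diary instruments together: "For daily e-diary scores (daily TNSS, daily TOSS, DMS, daily TSS, daily CSMS, RQLQ(S), PFASQ, and outdoor questionnaire), there are two baselines defined", namely pre-treatment and pre-season. Each baseline averages the scores in its window "except for the day of and one day following EEU challenge". One minimum follows for both: "The number of non-missing daily records must be at least 3 after excluding the records happening on the same day" as an EEU visit or the day after it. The section gives no separate minimum for an instrument that is not daily, and does not say what happens when fewer than 3 records remain.

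The schedule footnotes (Protocol 8.1.1, repeated in SAP 14.2) set the frequencies. Footnote 28: "RQLQ(S) is administered weekly starting at visit 2 (during screening baseline assessment period"). Footnote 29: "Pollen food allergy questionnaire (PFASQ) is administered every 2 weeks at baseline starting at visit 2". Visit 2 is the screening birch EEU challenge. On the run-in, footnote 25 says that diary data "should be obtained for an approximate 2-week period or longer (at minimum 1 week) starting after the screening birch EEU challenge" until randomization.

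SAP 7.1.2 makes RQLQ(S) change and percent change from each baseline secondary endpoints. SAP 14.1 analyses RQLQ(S) by the method of the row above it, which is the field-score ANCOVA. SAP 7.2.2 limits multiple imputation to day 29 endpoints.

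**The concern.** A minimum of 3 is undemanding for a score recorded every day. For a weekly or two-weekly form it becomes a requirement on the length of the run-in, and the planned run-in is shorter than that. The first form, due on the birch EEU day, is also one of the excluded days.

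In-season health-related quality of life is a stated secondary objective. A participant without a pre-treatment RQLQ(S) baseline has no change or percent change from that baseline. If the model carries that baseline as a covariate, the participant also drops out of the comparison of seasonal means. No imputation is planned that would restore them.

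**Working it through.** **Inputs.** Form interval f: 7 days for RQLQ(S), 14 for PFASQ, 1 for the daily scores (footnotes 24, 28, 29, 30). Day 0 is visit 2. Excluded days are 0 and 1, plus the oak EEU day and the next day for participants who have that challenge. L is the number of days from visit 2 to dosing. The minimum of 3 is a threshold rather than a calculated figure, so there is no plan figure to reproduce.

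**Formulas.**
- First form on day 0: usable weekly or two-weekly records = floor(L/f) if a record on the dosing day counts, or floor((L−1)/f) if it does not.
- Most favourable timing, first form on day 2 and dosing day counted: floor((L−2)/f) + 1.
- An oak EEU on day 7 removes one further RQLQ(S) record when the first form is on day 0.

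**RQLQ(S).**
- L = 14, first form on day 0: floor(14/7) = 2, or floor(13/7) = 1. Favourable timing: floor(12/7) + 1 = 2.
- L = 21, first form on day 0: floor(21/7) = 3, or floor(20/7) = 2.
- L = 16, favourable timing: floor(14/7) + 1 = 3. This is the shortest run-in that can reach 3.
- L = 28 with oak EEU on day 7: 4 − 1 = 3, dosing day counted.

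**PFASQ.**
- L = 14: floor(14/14) = 1, or floor(13/14) = 0.
- L = 42: floor(42/14) = 3, or floor(41/14) = 2.
- L = 30, favourable timing: floor(28/14) + 1 = 3. This is the shortest run-in that can reach 3.

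**Usable pre-treatment records.** The ranges cover the dosing-day choice and, outside the oak column, the timing of the first form.

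| Run-in (days) | RQLQ(S) | RQLQ(S), oak EEU on day 7 | PFASQ |
|---|---|---|---|
| 7 | 0–1 | not applicable | 0–1 |
| 14 | 1–2 | 0–1 | 0–1 |
| 21 | 2–3 | 1–2 | 1–2 |
| 28 | 3–4 | 2–3 | 1–2 |
| 42 | 5–6 | 4–5 | 2–3 |

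The oak column starts at 14 days because footnote 6 recommends about 1 week between challenges and about 1 week between a challenge and dosing. Daily scores give 5–6 usable records at 7 days and reach 3 within 4–5 days, so the rule works for them.

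**Role of the exclusion.** If the visit 2 record were kept, a 14-day run-in could give 3 RQLQ(S) records (days 0, 7 and 14). Under the exclusion, no timing variant reaches 3 at 14 days or fewer.

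**Pre-season baseline.** Visit 10 is nominally day 127 and dose 2 day 155, with the season anticipated 0 to 3 weeks later. The window is therefore 155 − 127 = 28 days, up to 28 + 21 = 49. With records from visit 10 to the day before the season, that gives 4–7 RQLQ(S) records, so the rule is met, and 2–4 PFASQ records. A window of 7–14 days gives only 1–2 RQLQ(S) records, or 0–1 if visit 10 is combined with an EEU visit.

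**The case against.** **The run-in is not capped at 2 weeks.** Footnote 25 allows longer, and screening may last up to 10 weeks (Protocol 5.1; one sentence there says 14). A reader might infer from the nominal schedule that most quality-of-life baselines would be missing. The documents do not support that: if run-ins were all about 14 days, essentially every pre-treatment RQLQ(S) baseline would fail, while at 28 days or more nearly all could pass. This objection stands in full.

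**The wording may not be meant for weekly forms.** The minimum refers to daily records, and Section 11.1 opens with a default of the latest valid value before dosing. However, that default applies only where nothing else is specified, and the section then names RQLQ(S) and PFASQ under its daily scores. If the minimum is not meant for them, they have none. Either reading needs new text.

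**Loss from the seasonal-mean model is inferred.** SAP Table 3 names the pre-treatment baseline covariate for field symptom scores, and its footnote 4 does not list RQLQ(S). The link is the cross-reference in SAP 14.1, and the SAP does not say how a missing covariate is handled. That consequence should stay conditional.

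**Importance is limited.** RQLQ(S) lies outside the hierarchy in SAP 8.2. PFASQ relates to an exploratory endpoint on food reactions, with no change from baseline listed. Both points stand. The pre-treatment records also predate dosing, so the main harm is to precision and representativeness.

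**Conclusion.** The point holds for the pre-treatment RQLQ(S) baseline. Applied literally, SAP 11.1 leaves it missing for participants whose run-in is under about 3 weeks, or about 4 weeks where the oak EEU coincides with the day-7 form; with favourable timing the limit falls to 16 days. Those participants leave the analyses of change and percent change from pre-treatment baseline. If the field-score ANCOVA applies as SAP 14.1 indicates, they leave the seasonal-mean model too.

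The counts assume forms completed on schedule from visit 2. The share of participants affected cannot be stated. The pre-season RQLQ(S) baseline passes on the nominal schedule and fails only in short windows. PFASQ fails the minimum more often, with no listed inferential analysis at stake. Neither the primary endpoint nor any alpha-controlled test is touched.

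**What to change.** In SAP 11.1, restrict the 3-record minimum to the daily scores: TNSS, TOSS, TSS, DMS, CSMS and outdoor time. For RQLQ(S) and PFASQ, define each baseline, pre-treatment and pre-season, as the mean of all available records in its window after the existing EEU-day exclusion, with a minimum of 1 record.

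The cost is SAP wording only, with no new data. It is best settled before unblinding, so that the rule is not improvised in programming. Baselines resting on 1 or 2 questionnaires will be slightly noisier. RQLQ(S) has a 1-week recall (Protocol 8.2.2.8), so an early record may still cover the chamber day even though it was not completed on an excluded day. A run-in of barely 1 week can still leave no usable RQLQ(S) record, as can one of up to 2 weeks for PFASQ, so the text should also say how a participant with none is handled.
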